7.1.3.1 Screening Period (Days -56 to 0) (For Cohort 2 only)

If the screening period is expected to be prolonged due to COVID-19 related issues, site follow-up with the medical monitor and investigator is required to determine if the screening period can be extended for another two weeks. Determination will be assessed on a case-by-case basis. During this allowed two-week extension period, it is anticipated that no additional testing and assessments will be required. If the screening period is extended beyond two weeks, additional assessments, including but not limited to safety labs, will be required.

Day -56 to Day -35/Clinic Visit S-1

Cohort 2 patients will undergo a Screening Visit up to 56 days prior to the planned first day of study treatment. Screening procedures and assessments are as follows:

- Obtain written informed consent
- Assess inclusion/exclusion criteria ([Section 7.2](#))
- Record demographics
- Document concomitant medications
- Medical and surgical history (date of diagnosis of PFIC Type, prior investigational medications for PFIC, historical liver function test [LFT] values, any surgery performed, any other diagnosis, and historical liver biopsy data)
- For patients with episodic forms of PFIC (i.e., BRIC), collect information on frequency, duration, and severity of flares within the last 6 months at a minimum, and within the last 5 years, if possible. If available, historical data on serum bile acid levels and pruritus should be collected
- Collect, if available, past confirmatory clinical genetic laboratory report for PFIC, including BRIC, type and send to central reader for review. If a historical report is equivocal, unavailable, or unobtainable, a blood sample for clinical genetic testing will be collected to determine eligibility ([Section 10.2.4](#))
- Physical examination ([Section 10.2.5](#)) and vital signs ([Section 10.2.6](#))
- Skin examination ([Section 10.2.5](#))

- eDiary training and compliance requirements; caregivers and/or patients begin daily recording of pruritus using the eDiary ([Appendix 2](#))
- Clinical chemistry ([Section 10.2.1](#))
- Serum bile acids ([Section 9.2.1](#))
- Serum pregnancy test for girls who have reached menarche. Please see [Appendix 6](#) for contraceptive requirements
- AE monitoring

Day -28 to Day -7/Clinic Visit S-2

A second Screening Visit will be performed for patients in Cohort 2. Screening procedures and assessments are as follows:

- Review concomitant medications
- Vital signs ([Section 10.2.6](#))
- Albireo PRO/ObsRO eDiary review for compliance
- Serum bile acids ([Section 9.2.1](#))
- International normalized ratio (INR)
- Urine pregnancy test for girls of who have reached menarche
- AE monitoring
- Clinical chemistry retest (if applicable)

7.1.3.2 Treatment Period

Study Day 1/Visit 1

For Cohort 1, patients will undergo a Screening/Inclusion Visit that coincides with Visit 9 of Study A4250-005.

For Cohort 1: Obtain written informed consent

For Cohort 2: Albireo PRO/ObsRO eDiary review for compliance and eligibility criteria (see Inclusion Criteria 4 [Cohort 2, excluding BRIC], [Section 7.2.1](#)).

The following procedures will be conducted for both cohorts:

- Assess inclusion/exclusion criteria ([Section 7.2](#))
- Document concomitant medications
- Physical examination ([Section 10.2.5](#)) and vital signs ([Section 10.2.6](#))
- Skin examination ([Section 10.2.5](#))

- Albireo PRO/ObsRO eDiary training, compliance requirements, and instructions to continue recording of pruritus ([Appendix 2](#))
- Clinical chemistry, hematology, and urinalysis ([Section 10.2.1](#))
- Serum bile acids ([Section 9.2.1](#))
- p-C4 and autotaxin
- Alfa-fetoprotein (AFP)
- Vitamins A, E, and 25-hydroxy vitamin D ([Section 10.2.1](#))
- Abdominal ultrasound ([Section 10.2.7](#))
- Fibroscan, where available ([Section 9.2.8](#))
- Administer QoL (Pediatric Quality of Life Inventory [PedsQL]) questionnaire
- Serum pregnancy test for girls who have reached menarche (only for patients in Cohort 1). Please see [Appendix 6](#) for contraceptive requirements
- Patient/caregiver/clinician complete the patient global impression of symptoms (PGIS) and the patient global impression of change (PGIC)
- AE monitoring
- Study drug is dispensed

Week 4/Visit 2

The following procedures and assessments will be conducted:

- Document concomitant medications
- Vital signs ([Section 10.2.6](#))
- Skin examination ([Section 10.2.5](#))
- Albireo PRO/ObsRO eDiary review for compliance
- Clinical chemistry and hematology ([Section 10.2.1](#))
- INR
- Serum bile acids ([Section 9.2.1](#))
- p-C4 and autotaxin
- Patient/caregiver/clinician complete the PGIS and the PGIC
- Urine pregnancy test for girls who have reached menarche
- AE monitoring
- Evaluation of study drug compliance

- Study drug is dispensed

Week 8/Telephone contact 1

- A study nurse will contact patients via telephone for AE monitoring 4 weeks after Visit 2, at Week 8

Week 12/Visit 3

As of Protocol Amendment 6.1 UK, patients entering Cohort 2 will start treatment at 40 µg/kg/day with the possibility to dose escalate to 120 µg/kg/day after 12 weeks (Visit 3) if there is no improvement in pruritus based on investigator judgment.

The following procedures and assessments will be conducted (all patients):

- Document concomitant medications
- Physical examination ([Section 10.2.5](#)) and vital signs ([Section 10.2.6](#))
- Skin examination ([Section 10.2.5](#))
- Albireo PRO/ObsRO eDiary review for compliance
- Clinical chemistry and hematology ([Section 10.2.1](#))
- INR
- Serum bile acids ([Section 9.2.1](#))
- Vitamins A, E, and 25-hydroxy vitamin D ([Section 10.2.1](#))
- Patient/caregiver/clinician complete the PGIS and the PGIC
- Urine pregnancy test for girls who have reached menarche
- AE monitoring
- Evaluation of study drug compliance; dosage form acceptability questions will be asked of the caregiver and/or patient
- Study drug is dispensed

Week 18/Telephone contact 2

- A study nurse will contact patients via telephone for AE monitoring 6 weeks after Visit 3, at Week 18

Weeks 22 and 46/Visits 4 and 7

The following procedures and assessments will be conducted:

- Document concomitant medications
- Vital signs ([Section 10.2.6](#))
- Albireo PRO/ObsRO eDiary review for compliance
- INR
- Serum bile acids ([Section 9.2.1](#))
- Vitamins A, E, and 25-hydroxy vitamin D ([Section 10.2.1](#))
- Urine pregnancy test for girls who have reached menarche
- AE monitoring

Weeks 24 and 48/Visits 5 and 8

The following procedures and assessments will be conducted:

- Document concomitant medications
- Skin examination ([Section 10.2.5](#))
- Physical examination (Section 10.2.5) and vital signs (Section 10.2.6)
- Albireo PRO/ObsRO eDiary review for compliance
- Clinical chemistry, hematology, and urinalysis (Section 10.2.1)
- Serum bile acids (Section 9.2.1)
- p-C4 and autotaxin
- AFP
- Abdominal ultrasound ([Section 10.2.7](#))
- Fibroscan, where available ([Section 9.2.8](#))
- Administer PedsQL questionnaire
- Patient/caregiver/clinician complete the PGIS and the PGIC
- Urine pregnancy test for girls who have reached menarche
- AE monitoring
- Evaluation of study drug compliance

- Study drug is dispensed

Weeks 30 and 54/Telephone contacts 3 and 5

- A study nurse will contact patients via telephone for AE monitoring 6 weeks after Visits 5 and 8, at Weeks 30 and 54, respectively

Weeks 36 and 60/Visits 6 and 9

The following procedures and assessments will be conducted:

- Document concomitant medications
- Vital signs ([Section 10.2.6](#))
- Albireo PRO/ObsRO eDiary review for compliance
- Clinical chemistry and hematology ([Section 10.2.1](#))
- INR
- Vitamins A, E, and 25-hydroxy vitamin D (Section 10.2.1)
- Serum bile acids ([Section 9.2.1](#))
- Urine pregnancy test for girls who have reached menarche
- AE monitoring
- Evaluation of study drug compliance; dosage form acceptability questions will be asked of the caregiver and/or patient (only at Visit 6)
- Study drug is dispensed

Weeks 42 and 66/Telephone contacts 4 and 6

- A study nurse will contact patients via telephone for AE monitoring 6 weeks after Visits 6 and 9, at Weeks 42 and 66, respectively

Week 70/Visit 10

The following procedures and assessments will be conducted:

- Document concomitant medications
- Vital signs ([Section 10.2.6](#))
- Albireo PRO/ObsRO eDiary review for compliance
- Serum bile acids ([Section 9.2.1](#))
- INR
- Vitamins A, E, and 25-hydroxy vitamin D (Section 10.2.1)
- Urine pregnancy test for girls who have reached menarche

- AE monitoring

7.1.3.3 End of Treatment/Early Termination/Start of Optional Extension Period

Week 72/Visit 11

The last dose of study drug will be administered in the morning the day before the visit and the following assessments will be performed:

- Document concomitant medications
- Physical examination ([Section 10.2.5](#)) and vital signs ([Section 10.2.6](#))
- Skin examination ([Section 10.2.5](#))
- Albireo PRO/ObsRO eDiary review for compliance
- Clinical chemistry, hematology, and urinalysis ([Section 10.2.1](#))
- Serum bile acids ([Section 9.2.1](#))
- p-C4 and autotaxin
- AFP
- Abdominal ultrasound ([Section 10.2.7](#))
- Fibroscan, where available ([Section 9.2.8](#))
- Administer PedsQL questionnaire
- Urine pregnancy test for girls who have reached menarche
- Patient/caregiver/clinician complete the PGIC and PGIS
- AE monitoring
- Evaluation of study drug compliance; dosage form acceptability questions will be asked of the caregiver and/or patient
- Liver biopsy (if required; see [Section 9.2.10](#))
- Patient/Caregiver decide whether to continue A4250 treatment
- Dispensing of drug for optional Extension Period (if applicable)

7.1.3.4 Follow-up Visit

Week 76/Visit 12 (Patients/Caregivers not participating in Optional Extension Period)

Patients will return to the study site 28 days after Visit 11 or the last dose of study drug (for those patients who prematurely withdraw) for the following assessments:

- Document concomitant medications
- Vital signs ([Section 10.2.6](#))

- Albireo PRO/ObsRO eDiary review for compliance
- Clinical chemistry and hematology ([Section 10.2.1](#))
- INR
- Serum bile acids ([Section 9.2.1](#))
- Urine pregnancy test for girls who have reached menarche
- AE monitoring

7.1.3.5 Optional Extension Period

Week 88 and every 16 weeks thereafter up to commercial availability of drug

- Document concomitant medications
- Vital signs ([Section 10.2.6](#))
- Clinical Chemistry (Section 10.2.1)
- Serum bile acids (Section 9.2.1)
- Vitamins A, E, and 25-hydroxy vitamin D (Section 10.2.1)
- INR
- Urine pregnancy test for girls who have reached menarche
- Administer PedsQL questionnaire
- Patient/caregiver/clinician complete the PGIS and the PGIC
- Evaluation of study drug compliance
- Study drug is dispensed
- AE monitoring

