Methodology: This is a Phase 3, multi-center, open-label extension study to investigate the long-term efficacy and safety of a 120 µg/kg/day daily dose of A4250 in patients with PFIC, including episodic forms also referred to as benign recurrent intrahepatic cholestasis (BRIC). Cohort 1 will consist of children with PFIC Types 1 and 2 who have participated in study A4250-005. Cohort 2 will consist of approximately 60 patients with PFIC who have elevated serum bile acids and cholestatic pruritus and who either (1) do not meet eligibility criteria for Study A4250-005 (PEDFIC 1) or (2) are eligible for enrolment in A4250-005 after recruitment of study A4250-005 has been completed. Up to 40 patients post biliary diversion surgery are allowed to participate in Cohort 2. Eligible patients will be enrolled into this open-label extension study and treated with a daily dose of 40 µg/kg/day ¹ or 120 µg/kg/day of A4250 for 72 weeks, or 40 µg/kg/day for the first 12 weeks followed by 120 µg/kg/day for the remaining 60 weeks ¹ . Patients not tolerating the 120 µg/kg/day dose after a minimum of 1 week will have the option to down-titrate to a lower dose (40 µg/kg/day). The patient should return to the higher dose as soon as deemed appropriate by the investigator. More than one upward dose titration (from 40 µg/kg/day directly to 120 µg/kg/day) for the same event is not recommended. Any dose titration should be done in consultation with the sponsor Medical Monitor or designee.				

¹ As of Protocol Amendment 6.1 UK, patients entering Cohort 2 will start treatment at 40 µg/kg/day with the possibility to dose escalate to 120 µg/kg/day after 12 weeks if there is no improvement in pruritus based on investigator judgment.

Name of Sponsor/Company:	Name of Product:	Name of Active Ingredient:
Albireo AB	A4250	A4250

Patients who wish to continue receiving A4250 after 72 weeks, will have the option to remain on treatment until the drug is commercially available, provided continued use is supported by the risk-benefit profile and the subject has not been previously withdrawn or discontinued from the study.
 
The primary analysis will be performed after the last patient (from Cohort 1 or 2) completes the 72-week treatment period. Analyses during the extension period will consist of safety summaries and other evaluations on an ongoing basis per the schedule of assessment for the extension period.
		

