
pruritus assessments will be included in the analysis of this endpoint. Baseline will be defined as the average score from 14 days prior to treatment start in A4250-008 for AM and PM, respectively.
 
The change from baseline over the treatment period in serum bile acids will be analyzed mainly by using descriptive statistics. Fasting serum bile acids baseline will be calculated as the average of the pre-dose value in Study A4250-008 (Visit 1) and the previous visit (Visit 8 in study A4250-005) for Cohort 1. Fasting serum bile acids baseline will be calculated as the average of Visit S-2 and the pre-dose Visit 1 values in Study A4250-008 for Cohort 2. The end value is the average of the values at Weeks 70 and 72 in study A4250-008.
 
Descriptive statistics will be summarized for Cohort 1, Cohort 2 excluding BRIC, Cohort 2 BRIC, and combined Cohort 1 + Cohort 2 excluding BRIC. Within Cohort 1, the following subgroups will be presented: 'A4250 40 µg/kg/day (-005) to 120 µg/kg/day (-008)', 'A4250 120 µg/kg/day (-005) to 120 µg/kg/day (-008)', 'A4250 40 µg/kg/day (-005) and 120 µg/kg/day (-005) to 120 µg/kg/day (-008)', and 'placebo (-005) to 120 µg/kg/day (-008)'. Within Cohort 2 excluding BRIC, 3 subgroups ('40 µg/kg/day', '40 µg/kg/day to 120 µg/kg/day', and '120 µg/kg/day') will be presented. Cohort 1 Placebo to A4250 120 µg/kg/day will also be combined with Cohort 2 excluding BRIC for presentations. Change over time will also be displayed using graphical presentations (e.g., a spaghetti plot which illustrates the change in both Study A4250-005 and Study A4250-008 by treatment group in Study A4250-005).
 
Evaluation of Secondary and Exploratory Efficacy Variables:
 
All secondary and exploratory variables will be analyzed descriptively for categorical and continuous data, as applicable. For continuous data, the change from baseline will be analyzed in addition to the actual visit values. For categorical data, shift tables or frequency and percentages of patients will be presented as appropriate. Change in growth (Z-score, SD from P50 standard growth curve) will be analyzed by using one-sample T-test or Wilcoxon signed-rank test as appropriate. Change in growth (height/length for age, weight for age, mid-arm circumference and BMI) will also be displayed using graphical presentations.
 
A 95% confidence interval (CI) will be calculated for the proportion of patients with at least one event, i.e., bile diversion or liver transplantation or death. The upper boundary will be compared to the expected proportion of events, using the event probability estimated from the untreated reference population in an ongoing observational cohort study.
 
Time to first event, i.e., time to surgical bile diversion or liver transplantation or death, will be explored by descriptive statistics and Kaplan-Meier curves, which also will be used to make a comparison to the untreated reference population.
 
Evaluation of Safety Variables:
 
Safety data will be analyzed using descriptive statistics and summaries overall of SAEs, AEs, vital signs, clinical laboratory tests (hematology, clinical chemistry and urinalysis) and concomitant medication. Analyses will be performed using the full analysis set.
 
Sample Size Determination:
 
There is no formal hypothesis testing in this open label-study. Sample size for Cohort 1 was determined in Study A4250-005. For Cohort 1, patients will be enrolled following completion or participation of at least 12 weeks of Study A4250-005. The expected proportion of patients with at least one event, i.e., surgical bile diversion or liver transplantation or death, in untreated patients is expected to be high enough to be able to detect an improvement after A4250 treatment. If the expected proportion with at least one event is estimated to be 30% in the study population of Cohort 1, and then if the proportion of patients with at least one event during A4250 long-term treatment are shown to be only 10% in the study, the power is approximately 89% to 96% (1-sided test, alpha=2.5%) for a CI with upper boundary <30% based on a sample size of n=48 to 60. The sample size of 60 patients for Cohort 2 was estimated based on the availability of target patient population to evaluate the therapeutic benefit for those patients.
		

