7 INVESTIGATIONAL PLAN

7.1 Overall Study Design and Plan

7.1.1 Description

This is a Phase 3, multi-center, open-label extension study to investigate the long-term efficacy and safety of a 120 µg/kg daily dose of A4250 in patients with PFIC, including episodic forms also referred to as BRIC. Cohort 1 will consist of children with PFIC Types 1 and 2 who have participated in Study A4250-005. Cohort 2 will consist of approximately 60 patients with any type of PFIC who have elevated serum bile acids and cholestatic pruritus and who either (1) do not meet eligibility criteria for Study A4250-005 (PEDFIC 1) or (2) are eligible for enrolment in A4250-005 after recruitment of study A4250-005 has been completed. Up to 40 patients post biliary diversion surgery are allowed to participate in Cohort 2.

The study includes a 72-week Treatment Period and a 4-week Follow-up Period. Patients who wish to continue receiving A4250 after 72 weeks will have the option to remain on treatment in an extension period with visits every 16 weeks until the drug is commercially available, provided continued use is supported by the risk-benefit profile and the subject has not been previously withdrawn or discontinued from the study. In that case the 4-week Follow-up Period will not occur.

The study data will be reviewed periodically (approximately on a quarterly basis) by a Data Safety and Monitoring Board (DSMB) until the last patient reaches 72 weeks.

Eligible patients will be enrolled into this open-label extension study and treated with a daily dose of 40 µg/kg/day³ or 120 µg/kg/day of A4250 for 72 weeks, or 40 µg/kg/day for the first 12 weeks followed by 120 µg/kg/day for the remaining 60 weeks³. Patients not tolerating the 120 µg/kg/day dose after a minimum of 1 week for reasons other than new liver findings and severe diarrhea, as described in [Section 10.2.2](#), will have the option to down-titrate to a lower dose (40 µg/kg/day). The patient should return to the higher dose as soon as deemed appropriate by the investigator. More than one upward dose titration (from 40 µg/kg/day directly to 120 µg/kg/day) for the same event is not recommended. Any dose titration should be done in consultation with the sponsor Medical Monitor or designee.

Patients participating in the optional extension period will continue on a daily dose of 40 µg/kg/day or 120 µg/kg/day of A4250 with the option to down-titrate to a lower dose (40 µg/kg/day).

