Vitamins A^d, E, and 25-hydroxy vitamin D	X	X
International normalized ratio	X	X
Urine pregnancy^e	X	X
Adverse events^f	X	X
Study drug compliance evaluated	X	X
Study drug dispensed^g	X	
QoL questionnaire (PedsQL)	X	X
Patient/Caregiver/Clinician Patient Global Impression of Change	X	X
Patient/Caregiver/Clinician Patient Global Impression of Symptoms	X	X

^a Includes current medications.
^b Includes blood pressure, pulse, respiratory rate, temperature, height/length (using a certified stadiometer), mid-arm circumference (3 repeat measures), and body weight (using a certified weight scale). Body mass index will be calculated.
^c See [Table 4](#) for detailed parameters.
^d Patients will fast (only water intake is permissible) for at least 4 hours prior to the collection of samples for serum bile acids and vitamin A.
^e For girls who have reached menarche.
^f For hepatic adverse events and/or liver decompensation, a PK sample should be collected as close to the onset of the event as possible.
^g Study drug will be taken once daily throughout the extension period.

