7.1.3.6 Optional Extension Period End of Treatment

Upon commercial availability, patients should complete the End of Treatment (EOT) visit before starting commercial drug. For patients who decide to withdraw from the optional extension period prior to commercial availability, patients should immediately return to the site for the following EOT assessments:

- Document concomitant medications
- Vital signs ([Section 10.2.6](#))
- Clinical Chemistry (Section 10.2.1)
- Serum bile acids (Section 9.2.1)
- Vitamins A, E, and 25-hydroxy vitamin D (Section 10.2.1)

- INR
- Urine pregnancy test for girls who have reached menarche
- Administer PedsQL questionnaire
- Patient/caregiver/clinician complete the PGIS and the PGIC
- Evaluation of study drug compliance
- AE monitoring

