8.2 Administration of Study Drug

Patients will be dosed with 120 µg/kg/day or 40 µg/kg/day⁴ for 72 weeks or 40 µg/kg/day for the first 12 weeks followed by 120 µg/kg/day for the remaining 60 weeks⁴. Patients not tolerating the 120 µg/kg/day dose after a minimum of 1 week, for reasons other than new liver findings and severe diarrhea, will have the option to down-titrate to a lower dose (40 µg/kg/day). They should return to the higher dose as soon as deemed appropriate by the investigator. More than one upward dose titration (from 40 µg/kg/day directly to 120 µg/kg/day) for the same event is not recommended. If, in the opinion of the investigator, a dose titration should be considered prior to the 1 week minimum, the investigator should consult with the Medical Monitor or designee. Any dose titration should be done in consultation with the sponsor Medical Monitor or designee.

Study drug will be dispensed to the patient at defined intervals from Visit 1 through Visit 9, together with instructions on how to store and take the drug. Study drug administration data, including whether each patient took each dose or partial doses of study drug, whether there were any delayed or missed doses, and whether the capsule was opened or swallowed whole, will be documented through the diaries and transferred to the study database.

⁴ As of Protocol Amendment 6.1 UK patients entering Cohort 2 will start treatment at 40 µg/kg/day with the possibility to dose escalate to 120 µg/kg/day after 12 weeks if there is no improvement in pruritus based on investigator judgment.

Patients participating in the optional extension period will continue at the same dose as at the end of the 72-week treatment period (120 µg/kg/day or 40 µg/kg/day). Patients not tolerating the 120 µg/kg/day dose at any time throughout the extension period will have the option to down-titrate to a lower dose (40 µg/kg/day) following consultation with the sponsor Medical Monitor or designee. Patients should return to the higher dose as soon as deemed appropriate by the investigator. More than one upward dose titration (from 40 µg/kg/day directly to 120 µg/kg/day) for the same event is not recommended.

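### UK optional extension: daily dosing continues after Week 72 with no scheduled hematology; one added tube at existing draws would be a cheap, low-yield improvement

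*Protocol*

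**What the plan says.** The protocol file holds a Sweden version and a UK version. Only the UK version has an optional extension.

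- **Dosing.** UK Section 8.2: "Patients participating in the optional extension period will continue at the same dose as at the end of the 72-week treatment period". A footnote to UK Table 2 adds: "Study drug will be taken once daily throughout the extension period".
- **Visits.** UK Section 7.1.3.5 sets them at "Week 88 and every 16 weeks thereafter up to commercial availability of drug". UK Section 7.1.3.6 adds a closing visit: "patients should complete the End of Treatment (EOT) visit before starting commercial drug".
- **Blood tests at these visits.** UK Table 2 and both sections list clinical chemistry, serum bile acids, vitamins A, E and 25-hydroxy D, and INR. None lists hematology.
- **Week 76.** For patients who enter the extension, UK Section 7.1.1 says: "In that case the 4-week Follow-up Period will not occur". That follow-up visit includes "Clinical chemistry and hematology" (UK Section 7.1.3.4).
- **Analysis.** The UK synopsis says: "Analyses during the extension period will consist of safety summaries and other evaluations on an ongoing basis". The same sentence then ties these analyses to the extension's own assessment schedule. The safety paragraph of the synopsis plans "summaries overall of SAEs, AEs, vital signs, clinical laboratory tests (hematology, clinical chemistry and urinalysis") for the study overall.

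**The concern.** The patients with the longest exposure are the ones who stop having scheduled blood counts. A patient who stops drug at Week 72 has a further count at Week 76. A patient who stays on drug has none, not even at the closing visit. No remaining scheduled test measures hemoglobin: in the Sweden version's Table 3 it belongs to the hematology panel, and INR does not substitute for it.

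Sweden Sections 10.2.2.4 and 10.2.2.6 use a hemoglobin fall of about 2 g/dL as a trigger for discussion or for evaluation of fecal blood loss, and Section 10.2.2.6 names hematology assessments as one of two routes for finding iron deficiency anemia. If the UK text is the same, that trigger has no scheduled measurement behind it after Week 72. Reported blood in stool would remain a trigger, but it needs someone to notice it. What is at stake is a gradual, symptom-free hemoglobin fall in a population where Cohort 2 may include clinically significant portal hypertension. The 72-week efficacy analysis is not affected.

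**Working it through.** **1. Is the omission real or a PDF reading gap?** Appendix 7 (seen in the Sweden copy) has a block for the extension visits. Its tubes are chemistry/AFP 1.1, bile acid 1.1, vitamins A and E 2.5, vitamin D 1.1 and INR 1.4 mL:

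1.1 + 1.1 + 2.5 + 1.1 + 1.4 = 7.2 mL, which is the printed total.

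The vitamin tube reads 2.1 mL in part of the extracted appendix. That value would give 6.8 mL, so 2.5 mL, as printed for the earlier visits, is the right reading. The total is fully explained without an EDTA hematology tube, so the omission is real and matches UK Table 2 and both visit lists.

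**2. Scheduled counts before and after Week 72 (UK Table 1).** Hematology falls on Day 1 and Weeks 4, 12, 24, 36, 48, 60 and 72, which is 8 counts.

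- Gaps: 4, 8, 12, 12, 12, 12, 12 weeks; nominal maximum 12.
- With ±7-day windows: (84 + 14)/7 = 14 weeks.
- After Week 72 in the extension: 0 counts.

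**3. How many draws could a change still reach?** The protocol gives neither the length of the extension nor the number of UK patients in it. Assume that the planned study period (Q3 2018 to Q3 2023) covers the extension.

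- Earliest possible entrant: 1 July 2018 + 504 days = 17 November 2019 (Week 72).
- From there to 30 September 2023: 1413 days; 1413/112 = 12.6, so 12 sixteen-weekly visits.
- From there to the protocol date, 11 February 2022: 817 days; 817/112 = 7.3, so 7 of those visits had already passed.
- Still reachable: 12 − 7 = 5 visits, plus EOT = **6 draws**.
- Patient starting on the protocol date: 11 February 2022 + 504 days = 30 June 2023; 92 days remain, fewer than 112, so EOT only = **1 draw**.

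Earlier commercial availability shortens all of this.

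**4. After the fix.**

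- Largest nominal gap: 16 weeks; with windows, (112 + 14)/7 = 18 weeks.
- Draw volume: 7.2 + 1.0 = 8.2 mL.
- Visit 3 for comparison: 1.1 + 1.0 + 1.4 + 1.1 + 2.5 + 1.1 = 8.2 mL. Visits 6 and 9 have the same total.
- Added blood per patient: 1 to 6 draws × 1.0 mL = 1.0 to 6.0 mL.

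**The case against.** The strongest reply is that this is a deliberate and coherent reduction. Urinalysis, ultrasound, Fibroscan, physical and skin examination, p-C4, autotaxin and the diary are dropped as well. The extension only bridges to commercial supply of a drug already approved by the EMA and FDA and minimally absorbed. UK Section 5.3.2 reports no hematology trend or signal in patients treated for 48 weeks or longer. Chemistry, vitamins and INR continue, adverse events are collected at every visit, and extra clinic visits are allowed. In the Sweden version, patients leave after Week 76 with no further study blood tests, so the UK extension adds monitoring. Visit 12 is an off-drug follow-up with a different purpose. Most of this stands. It makes the expected yield low and rules out calling the schedule an error. It does not supply a scheduled hemoglobin value.

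Three stronger readings are tempting and should not be drawn:

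- **That the synopsis promises extension hematology which the schedule fails to deliver.** It does not. The extension analyses are defined by the extension schedule. The safety paragraph describes the study overall, is fed by the counts to Week 72, and also names urinalysis, which the extension lacks too.
- **That up to 13 draws per patient are at stake.** Counting 12 visits plus EOT for the earliest entrant includes 7 visits that precede this version.
- **That the UK safety rules are left unworkable.** The 2 g/dL triggers, and the eosinophilia arm of the liver interruption criteria, are visible only in the Sweden version. The UK contents list the same headings, but the UK text of Section 10 is not in the file, and the two versions differ elsewhere under identical headings (Section 7.2.2, for example). The eosinophilia arm also needs a bilirubin and transaminase rise, which the continuing chemistry would show.

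**Conclusion.** The point holds as a cheap improvement, between optional and a low-priority recommendation. In the UK extension, scheduled hematology falls from 8 counts by Week 72 to none while daily dosing continues. A symptom-free hemoglobin fall then has no routine detection.

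The size is modest: about 1 to 6 draws per extension patient from the date of this version, assuming the planned study period bounds the extension. The number of patients is unknown. The link to the 2 g/dL trigger is conditional on UK Section 10.2.2 matching the Sweden text. The reduced panel is internally consistent, and the expected yield is low. The argument is that the measurement costs very little at a venipuncture already taking place in the longest-exposed patients.

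**What to change.** - UK Table 2: add a Hematology row, with differential, marked in both columns (every 16 weeks and extension EOT).
- UK Sections 7.1.3.5 and 7.1.3.6: change the clinical chemistry item to clinical chemistry and hematology.
- Appendix 7, extension block: add one 1.0 mL EDTA tube and correct the total from 7.2 to 8.2 mL.

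The cost is one assay and 1.0 mL of blood per existing draw. It needs no added visit or procedure and leaves the 72-week analysis unchanged. The tube volumes are those of Appendix 7 in the Sweden copy and should be confirmed against the UK appendix.
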